### **Outpatient dose titration period**

#### **Visit 3 (Outpatient dose titration period Visit)**

During the outpatient dose titration phase, patients continue to receive sacubitril/valsartan or enalapril. There are 3 available doses of study drug administered twice daily. All subsequent dose changes during the medication titration period is selected using a dose titration algorithm based on systolic blood pressure (SBP) (**Figure 1**). Clinician-investigators are encouraged to up titrate sacubitril/valsartan to target dose (i.e., dose level 3) as tolerated during the medication titration phase. every attempt should be made to complete the dose titration period within 8 weeks regardless of any down-titration that may occur.

**Figure 1 dose titration algorithm**

**Follow-up period**

**Visit 4 (Follow-up Visit)**

Follow-up visits are scheduled for Weeks 4, 12 and 24. Blood and urine samples are sent to a central laboratory for hematology, chemistry, and serum biomarkers. Professionals use Philips IE33 ultrasound system (Philips Medical System, Bothell, Washington, USA) for echocardiographic measurements. In addition to the protocol-required visits, patients may be seen at any time throughout the study at the discretion of the investigator to investigate or follow any new lab abnormalities or adverse events. Monitoring of safety and tolerability will include: (1) hyperkalemia; (2) symptomatic hypotension; (3) increase in serum creatinine; (d) angioedema; and (e) adverse events and serious adverse events. If, in the opinion of the investigator, the patient cannot tolerate the target dose of study drug, the investigator should consider whether non-life saving medication (e.g., CCBs, nitrates,  $\alpha$ -blockers) can be reduced to rectify the situation before considering reducing the dose of the study drug to the lower dose level. The dose of background disease modifying drugs, such as  $\beta$ -blockers and mineralocorticoid receptor antagonists, should not be reduced to facilitate maintenance of study drug. If the situation is not rectified despite adjusting/discontinuing nonlife-saving medications or if adjusting non-life-saving concomitant medications is not possible, patients who no longer tolerate the target dose at any time during the course of the trial can be down-titrated to the lower dose level at the investigator’s discretion (please refer to Figure 1 for dose levels available for titration). However, every attempt should be made to re-challenge the patients so that they are kept on the maximal tolerated dose of study drug for as long a duration as possible throughout the outpatient dose titration and follow-up period of the trial. Please refer to Section 6.4.3 for a guidance on study drug dose adjustment.

**Primary assessment:**

- NT-proBNP
- LVEF
- LVEDV
- LVESV

**Secondary assessments:**

- Death
- Reinfarction
- hospitalization for heart failure or outpatient heart failure
- arrhythmia
- stroke

**Safety assessments:**

- AEs and SAEs
- hypotension
- Angioedema
- Laboratory values
- Hyperkalemia

**Data analysis:** Analyses of the change from baseline in NT-proBNP and echocardiographic parameter was performed using an analysis-of-covariance model adjusted for baseline values. Logarithmic transformation is used for NT-proBNP, due to its skewed distribution.

The secondary efficacy variables will be analyzed using Kaplan-Meier estimates and Cox proportional hazards models. The hazard ratios, 95% confidence intervals, and two-sided P values are calculated using the model to adjust the following baseline prognostic factors: Age, gender, body mass index, total cholesterol, triglycerides, history of hypertension, diabetes and Previous smoking.

We will use Fisher's exact test to compare rates of Safety outcomes.

The targeted sample size mainly is driven by the LVEF of the primary composite endpoint. Assuming that the increase in LVEF is  $3\% \pm 6\%$ , the patients are included in the ratio 1:1 when  $\alpha=0.05$  and the test power is 80%, and the sample size for each group is predicted to be 64 cases.

## **1 Background**

Angiotensin receptor-neprilysin inhibitor (ARNI, Sacubitril/Valsartan) is superior to angiotensin-converting enzyme inhibitors (ACEI) on cardiac remodeling in patients with heart failure (HF). However, there is little data describing the effects of sacubitril/valsartan in patients with acute anterior ST-segment elevation myocardial infarction (STEMI). The objective is to assess the safety and efficacy of sacubitril/valsartan compared with Enalapril in patients with acute anterior STEMI after PCI.

This study is a single center, prospective, randomized, double-blind trial, planning to recruit patients with acute anterior STEMI at the Second Affiliated Hospital of Nanchang University. Patients are randomly assigned 1:1 to in-hospital initiation of sacubitril/valsartan and enalapril. The starting dose during the in-hospital initiation phase and all subsequent dose changes during the titration period is selected using a dose titration algorithm (Figure 1). Patients are followed up at 4, 12, and 24 weeks after discharge from the hospital, blood test and echocardiograph are performed. The primary efficacy outcomes are the changes in NT-proBNP concentrations and in echocardiographic parameters (LVEF, LVEDV, LVESV) from baseline through weeks 4, 12 and 24. Secondary outcomes include the incidence of a composite of death, reinfarction, hospitalization for heart failure or outpatient heart failure, arrhythmia, stroke. Safety endpoints are the incidence of angioedema, hypotension, renal insufficiency, and hyperkalemia.

## **2 Purpose and rationale**

The purpose of this study is to evaluate the effect of sacubitril/valsartan compared to enalapril in reducing the concentration of NT-proBNP and improving the main cardiac ultrasound parameters in patients with acute anterior STEMI after PCI.

## **3 Study goals and objectives**

### **3.1 Primary objective:**

The primary objective of this study is to test if sacubitril/valsartan is superior to enalapril in reducing the concentration of NT-proBNP and improving the main cardiac ultrasound parameters in patients with acute anterior STEMI after PCI.

### **3.2 Secondary objective:**

The Secondary objective of this study is to test if sacubitril/valsartan is superior to enalapril in reducing the incidence of cardiovascular events (a composite of death, reinfarction, outpatient HF or HF hospitalization, arrhythmia, and stroke).

## **4 Study design**

This study is a single-center, prospective, randomized, double-blind, parallel-group, two-arm, short-term trial to compare sacubitril/valsartan 200 mg bid to enalapril 10 mg bid in concentration of NT-proBNP reduction and main cardiac ultrasound parameters improvement in patients with acute anterior STEMI after PCI.

### **4.1 Justification of key elements of the study design**

#### **4.1.1 Selection of the primary endpoint**

We chose NT-proBNP as the primary endpoint in this study because natriuretic peptide concentrations are associated with adverse outcomes in patients with AMI. Although both ANP and BNP undergo degradation by neprilysin, the biologically inert NTproBNP, cleaved from proBNP along with BNP, is not a substrate for neprilysin degradation, and changes in this marker still reflect reduction in left ventricular wall stress even in the setting of neprilysin inhibition.

#### **4.1.2 Choice of enalapril as the comparator**

Major clinical trials have established ACEI treatment as the standard of care for RAAS blockade and are recommended by treatment guidelines as the treatment of choice for all patients with AMI, unless ACEI-intolerant. Since the ultimate goal of the sacubitril/valsartan development program is to replace ACEIs as the guideline-recommended RAAS based agent in HF, an ACEI has been selected as the control in this study. As a well-studied ACEI in HF, enalapril is used as the comparator in this study. Enalapril was studied in a number of previous large, outcome-driven studies, such as OVERTURE, CONSENSUS, SOLVD-Treatment, and SOLVD-Prevention.

Enalapril dose of 10 mg bid has been selected as the comparator target dose for this study based on its ability to reduce the risk of death or hospitalization as demonstrated in the SOLVD-Treatment study.

#### **4.1.3 sacubitril/valsartan dose and dosing regimen**

A strong rationale exists for the selection of sacubitril/valsartan 200 mg bid as the target dose.

Importantly, a dose of sacubitril/valsartan 200 mg bid delivers similar exposures of valsartan (assessed by AUC) as Diovan® 160 mg bid, the maximal approved Diovan® dose for HF after AMI and the dose recommended in international guidelines for the treatment of HF after AMI. In addition, biomarker analysis (increase in ANP and cGMP) indicates that this dose delivers approximately 90% of its maximal NEP inhibition. The biomarker data are also consistent with results obtained in a dose ranging study in HTN, which demonstrated additive effects of the ARB moiety and the NEPi moiety with sacubitril/valsartan 400 mg and 200 mg once daily, with a minimal incremental BP reduction from sacubitril/valsartan 200 mg/d to sacubitril/valsartan 400 mg/d. sacubitril/valsartan 400 mg/d and 200 mg/d were well tolerated in this study.

Rather than 400 mg once daily dosing of sacubitril/valsartan that was used in the HTN study, this dose will be split and sacubitril/valsartan will be dosed at 200 mg twice daily in the current study. This will ensure sustained NEP inhibition over 24 hours, which is thought to be critical for patients with HF after AMI. Furthermore, twice daily dosing will also mitigate the likelihood of hypotension, particularly in those with more severe HF impairment (NYHA III-IV).

#### **4.1.4 Duration of the study**

As planned, it is expected to be up to 18 months: a recruitment period of approximately 12 months and a minimal follow-up of 6 months.

## **4.2 Study visits**

### **4.2.1 Screening**

#### **Visit 1 (Screening Visit)**

All patients must provide informed consent before any study-specific procedure is performed. At Visit 1, patients' eligibility for entering the randomization period, including whether the patient's vital signs are stable after PCI, will be assessed by the investigator. Whether enalapril is included in the medicine used immediately after the operation. Screening potassium levels and eGFR will be assessed by sending blood samples to the central laboratory and only patients with the required values per the entry criteria will be eligible for entering the randomization period, which will begin at Visit 2.

### **4.2.2 Randomization**

#### **Visit 2 (Randomization Visit)**

Patients who have met all the inclusion criteria and none of the exclusion criteria at the end of the screening period will be randomized to either enalapril or sacubitril/valsartan in a 1:1 ratio. Patients randomized to enalapril continue to receive enalapril, while

patients randomized to sacubitril/valsartan discontinue enalapril to ensure a minimum 36-hour washout period prior to initiation of ARNi therapy. The first dose of sacubitril/valsartan is followed by 6 hours of monitoring for hypotension. After the condition is stable, patients can be discharged from the hospital at any point in time at the discretion of the clinician-investigator. The starting dose during the in-hospital initiation phase is selected using a dose titration algorithm based on systolic blood pressure (SBP) (Figure 1).

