### **Randomization**

#### **Visit 2 (Randomization Visit)**

Patients who have met all the inclusion criteria and none of the exclusion criteria at the end of the screening period will be randomized to either enalapril or Sacubitril/Valsartan in a 1:1 ratio. Patients randomized to enalapril continue to receive enalapril, while patients randomized to sacubitril/valsartan discontinue enalapril to ensure a minimum 36-hour washout period prior to initiation of ARNi therapy. The first dose of sacubitril/valsartan is followed by 6 hours of monitoring for hypotension. After the condition is stable, patients can be discharged from the hospital at any point in time at the discretion of the clinician-investigator. The starting dose during the in-hospital initiation phase is selected using a dose titration algorithm based on systolic blood pressure (SBP) (**Figure 1**).

[figure not shown]

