#### **4.2.4 Follow-up period**

##### **Visit 4 (Follow-up Visit)**

Follow-up visits are scheduled for Weeks 4, 12 and 24. Blood and urine samples are sent to a central laboratory for hematology, chemistry, and serum and urinary biomarkers. Professionals use Philips IE33 ultrasound system (Philips Medical System, Bothell, Washington, USA) for echocardiographic measurements. In addition to the protocol-required visits, patients may be seen at any time throughout the study at the discretion of the investigator to investigate or follow any new lab abnormalities or adverse events.

Monitoring of safety and tolerability will include: (1) hyperkalemia; (2) symptomatic hypotension; (3) increase in serum creatinine; (d) angioedema; and (e) adverse events and serious adverse events. If, in the opinion of the investigator, the patient cannot tolerate the target dose of study drug, the investigator should consider whether non-life saving medication (e.g., CCBs, nitrates,  $\alpha$ -blockers) can be reduced to rectify the situation before considering reducing the dose of the study drug to the lower dose level. The dose of background disease modifying drugs, such as  $\beta$ -blockers and mineralocorticoid receptor antagonists, should not be reduced to facilitate maintenance of study drug. If the situation is not rectified despite adjusting/discontinuing nonlife-saving medications or if adjusting non-life-saving concomitant medications is not possible, patients who no longer tolerate the target dose at any time during the course of the trial can be down-titrated to the lower dose level at the investigator's discretion (please refer to Figure 1 for dose levels available for titration). However, every attempt should be made to re-challenge the patients so that they are kept on the maximal tolerated dose of study drug for as long a duration as possible throughout the outpatient

dose titration and follow-up period of the trial. Please refer to Section 6.4.3 for a guidance on study drug dose adjustment.

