## 5 Population

### 5.1 Inclusion criteria

Patients eligible for inclusion in this study have to fulfill all of the following criteria:

1. Patients must give written informed consent before any assessment is performed
2. Outpatients  $\geq 18$  years of age, male or female
3. Had typical pain and Diagnosed as acute anterior STEMI according to electrocardiogram, high-sensitivity troponin, and coronary angiography
4. Systolic blood pressure  $\geq 100$ mmHg without symptoms of dizziness during the last 12 hours prior to randomization

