### **7.5.2 Vital signs**

Vital signs will be assessed at every visit. This will include BP and pulse measurements. BP will be measured by using a standard sphygmomanometer with an appropriate size cuff and the non-dominant arm in the sitting position after 5 minutes of rest.

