## **8 Safety monitoring**

### **8.1 Adverse events**

An AE is the appearance or worsening of any undesirable sign, symptom, or medical condition occurring after starting the study drug even if the event is not considered to be related to study drug. Study drug includes the investigational drug under evaluation and the comparator drug or placebo that is given during any phase of the study. Medical conditions/diseases present before starting study drug are only considered AEs if they worsen after starting study drug. Abnormal laboratory values or test results constitute AEs only if they induce clinical signs or symptoms, are considered clinically significant, or require therapy.

The occurrence of AEs should be sought by non-directive questioning of the patient at each visit during the study. AEs also may be detected when they are volunteered by the patient during or between visits or through physical examination, laboratory test, or other assessments.

All AEs must be recorded on the Adverse Events CRF with the following information:

1. the severity grade [mild, moderate, severe]
2. its relationship to the study drug(s) (suspected/not suspected)
3. its duration (start and end dates or if continuing at final exam)
4. whether it constitutes a serious adverse event (SAE)

An SAE is defined as an event which:

- is fatal or life-threatening
- results in persistent or significant disability/incapacity
- constitutes a congenital anomaly/birth defect
- requires inpatient hospitalization or prolongation of existing hospitalization, unless hospitalization is for:
  - routine treatment or monitoring of the studied indication, not associated with any deterioration in condition
  - elective or pre-planned treatment for a pre-existing condition that is unrelated to the indication under study and has not worsened since the start of study drug
  - treatment on an emergency outpatient basis for an event not fulfilling any of the definitions of a SAE given above and not resulting in hospital admission
  - social reasons and respite care in the absence of any deterioration in the patient's general condition
- is medically significant, i.e. defined as an event that jeopardizes the patient or may require medical or surgical intervention to prevent one of the outcomes listed above.

**Unlike routine safety assessments, SAEs are monitored continuously and have special reporting requirements; see Section 8.2.**

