## **10.5 Safety**

The safety and tolerability assessments are listed below:

- AEs and SAEs
- hypotension
- Angioedema
- Laboratory values
- Hyperkalemia
- Renal dysfunction

The assessment of safety will be based primarily on the frequency of adverse events, SAEs, and laboratory abnormalities. Other safety data will be summarized as appropriate.

The incidence of treatment-emergent adverse events (new or worsened) will be summarized by primary system organ class, preferred term, severity, and relationship to study drug. In addition, the incidence of death, SAEs, and AEs leading to discontinuation will be summarized separately by primary system organ class and preferred term.

Laboratory data will be summarized by presenting shift tables using extended normal ranges (baseline to most extreme post-baseline value), by presenting summary statistics of raw data and change from baseline values and by the flagging of notable values in data listings.

We will use Fisher's exact test to compare rates of Safety outcomes.

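### A 6-hour hypotension watch is prescribed for the sacubitril/valsartan arm only, and the between-arm comparison of hypotension rates takes no account of it

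*Protocol*

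**What the plan says.** The Visit 2 text, in the synopsis and again in section 4.2.2, treats the arms differently after randomization: "Patients randomized to enalapril continue to receive enalapril, while patients randomized to sacubitril/valsartan discontinue enalapril". It then adds for one arm: "The first dose of sacubitril/valsartan is followed by 6 hours of monitoring for hypotension". No counterpart is given for enalapril anywhere in the protocol.

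Hypotension is an outcome to be compared. Section 1 states: "Safety endpoints are the incidence of angioedema, hypotension, renal insufficiency, and hyperkalemia". Section 10.5 lists hypotension among the safety assessments and specifies: "We will use Fisher's exact test to compare rates of Safety outcomes". It does not restrict that comparison to time observed alike in both arms, and it does not separate events by how they were found.

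The observation that applies to both arms is set out elsewhere. Section 7.5.2: "Vital signs will be assessed at every visit". Section 8.1: "The occurrence of AEs should be sought by non-directive questioning of the patient at each visit during the study". Section 4.2.4: "Monitoring of safety and tolerability will include: (1) hyperkalemia; (2) symptomatic hypotension; (3) increase in serum creatinine".

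The synopsis and section 4 call the trial double-blind.

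**The concern.** A difference in rates can be read as a difference between drugs only if events are looked for equally hard in both arms. Here one arm has an added, directed search for the very event being compared, placed just after a drug is started. Section 8.1 counts adverse events from the start of study drug, so an event in that window can enter the sacubitril/valsartan total. A symptom-free fall of the same size in an enalapril patient has no prescribed search to find it.

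The entry sequence adds to the imbalance. Where enalapril was begun after PCI, those patients met their own first dose before randomization. Section 5.1 then admits only patients with systolic pressure of at least 100 mmHg "without symptoms of dizziness during the last 12 hours prior to randomization".

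At stake is one of four named safety endpoints, and one that section 6.4.3 uses to guide dose adjustment. An excess on sacubitril/valsartan could be partly drug effect and partly detection, and the data as planned would not show which.

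**Working it through.** **Step 1: patients per arm.** Section 10.6 assumes an LVEF difference of 3 with SD 6, α = 0.05 and 80% power, and states 64 per group. A two-sided t-test calculation gives 63.8, so 64 reproduces. Then 2 × 64 = 128, and 128 / 0.9 = 142.2 against the stated 142. That gives 142 / 2 = 71 per arm. The present point does not affect this figure.

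**Step 2: ascertainment side by side.**

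| Source of hypotension data | Sacubitril/valsartan | Enalapril |
|---|---|---|
| Blood pressure at visits (7.5.2) | yes | yes |
| Adverse event questioning at visits (8.1) | yes | yes |
| Symptomatic hypotension in follow-up (4.2.4) | yes | yes |
| Directed 6-hour watch after first dose (4.2.2) | yes | not stated |

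Only the last row differs, and it can only add events to the sacubitril/valsartan count. The direction of the detection bias is therefore fixed.

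**Step 3: what the size would be under assumptions.** The protocol gives no hypotension rate and no share of events that only a watch would find. Both are assumed here:
- *p*: the rate recorded by common means, equal in both arms (5%, 10%, 20%)
- *e*: the share of the remaining sacubitril/valsartan patients with an event found only by the watch (0, 3%, 5%, 10%)

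The recorded rate is p on enalapril and p + (1 − p)e on sacubitril/valsartan. For example, with p = 0.05 and e = 0.05 it is 0.05 + 0.95 × 0.05 = 0.0975. Expected counts are 71 × 0.0975 = 6.9 against 71 × 0.05 = 3.6, a ratio of 1.95. With e = 0.10 the rate is 0.145, the count 10.3 and the ratio 2.9.

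The chance of a significant result is the sum, over all pairs of counts (a, b), of Bin(a; 71, p + (1 − p)e) × Bin(b; 71, p), taken where the two-sided Fisher p-value is at most 0.05. Adding both directions:

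| p | e = 0 | e = 3% | e = 5% | e = 10% |
|---|---|---|---|---|
| 5% | 1.38% | 4.74% | 10.69% | 38.00% |
| 10% | 2.56% | 4.75% | 8.45% | 25.84% |
| 20% | 3.16% | 4.18% | 6.01% | 14.90% |

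Once e > 0, most of this lies against sacubitril/valsartan. At p = 10% and e = 5% it is 8.32% against and 0.13% in favour. The extra detected cases behind these figures are few: about 2 at e = 3%, 3 at 5%, and 6 to 7 at 10%.

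**The case against.** A reader might go further and infer that the comparison counts against sacubitril/valsartan by construction, with falls on enalapril going unseen and a false significant excess to be expected. The documents do not support that, for four reasons.

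- **Setting.** Both arms are in hospital at this stage, and Appendix 3 asks investigators, without regard to arm, to watch blood pressure closely. Routine readings may well catch falls on enalapril. This lessens the imbalance, but it does not give the enalapril arm an equivalent window.
- **Type of event.** Sections 4.2.4 and 6.4.3 and Appendix 3 speak of symptomatic hypotension. Under section 8.1, events volunteered between visits count, and abnormal findings count only if they cause symptoms, are clinically significant or need therapy. A symptomatic fall is therefore reportable in either arm, and the bias is mainly confined to silent readings. Because the safety lists in the synopsis and in sections 1 and 10.5 say plain hypotension, silent readings are not ruled out.
- **Model.** The rates are assumed. The model also supposes that enalapril patients have the same hidden falls. If patients who stay on enalapril truly have fewer, an excess in the window is partly a real effect of starting the other drug. This stands. It is also why window events should not simply be removed from the comparison, since that could hide genuine initiation hypotension.
- **Blinding.** If the blind held, the watch could not in practice be limited to one arm. But the text ties it to a named drug. That is a contradiction to be reconciled, and the double-blind label does not supply the missing enalapril window.

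It is also true that no confirmatory claim rests on this test. And although the statistical analysis plan, which is not shown, could define hypotension more closely, it can separate watch-only events only if they are identified when recorded.

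**Conclusion.** The point holds as a built-in direction of bias of unknown size. The protocol prescribes unequal detection of hypotension and compares its rate between arms without allowing for it.

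Under equal true rates of 5% to 20% and 71 per arm, the chance of p < 0.05 is below 5% if the watch adds events in 3% or fewer of the remaining patients, 6% to 11% at 5%, and 15% to 38% at 10%. With no watch-only events it is 1.4% to 3.2%. These figures rest on assumed rates and on equal hidden falls in both arms. They show when the matter becomes material. They do not predict a false finding.

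**What to change.** 1. Add a field to the adverse event form marking any hypotension found only during the 6-hour watch.
2. In section 10.5, keep the all-events rate. Add a between-arm comparison limited to ascertainment common to both arms from randomization: blood pressure at scheduled visits, and symptomatic or treated hypotension whenever it occurs, including during the watch.
3. Report watch-only events separately as a descriptive rate, and state that an excess made up of them will not be read as a between-arm drug difference.
4. Reconcile the arm-specific monitoring rule in section 4.2.2 and the synopsis with the double-blind statement. Which way is for the sponsor to decide.

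The cost is one extra analysis and one form field. Because the all-events rate stays, no first-dose event drops out of the safety report.
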